8.11. CONCOMITANT THERAPY

Axitinib is metabolised primarily by liver enzymes, in particular CYP3A4. All medication considered necessary for the patients' welfare and which is not expected to interfere with the evaluation of the

study drugs may be given at the discretion of the investigator. Concomitant medications must be recorded in the patient's source documentation, as well as the appropriate pages of the CRF.

Contraindicated concurrent medications include:

- Agents known to induce CYP3A4/5 or CYP1A2 including:
 - carbamazepine,
 - dexamethasone,
 - felbamate,
 - omeprazole,
 - phenobarbital,
 - amobarbital,
 - phenytoin,
 - primidone,
 - rifabutin,
 - rifampicin,
 - nevirapine,
 - St John's wort
 - rifapentine
- Agents known to inhibit CYP3A4/5 including:
 - grapefruit juice,
 - ketoconazole,
 - miconazole,
 - itraconazole,
 - erythromycin,
 - clarithromycin,
 - telithromycin,
 - verapamil,
 - indinavir,
 - saquinavir,
 - ritonavir,
 - nelfinavir,
 - lopinavir,
 - atazanavir,
 - amprenavir,
 - fosamprenavir
 - delavirdine
 - nefazodone
- Other approved or investigational systemic anticancer treatments, including chemotherapy, hormone therapy and immunotherapy
- Other investigational drugs

The use of potent antacids such as proton pump inhibitors (except those listed above) and histamine H₂ antagonists is permissible, if medically necessary. However, patients requiring chronic antacid therapy should avoid their use for 2 hours before and for 2 hours after taking axitinib tablets.

The contraindicated medications detailed above may only be used in exceptional circumstances and following written confirmation from the ICR-CTSU of the Chief Investigator's approval.

The current version of the SmPC should be used to assess whether any other concomitant medications are permissible.

8.12. SUBSEQUENT THERAPY

Participants for whom treatment is discontinued should be treated according to clinical circumstances and should be managed at the local clinician's discretion.

8.13. DRUG COMPLIANCE AND ACCOUNTABILITY

The study drug must not be used outside the context of the A-PREDICT protocol. Patients must be asked to bring all their trial medication every time they attend the clinic for the purposes of treatment compliance assessment and drug accountability. Every effort should be made to encourage patients to return the unused medication and empty packs/bottles. The unused tablets should be collected by the investigator/study nurse and counted to ascertain patient compliance, medication will then be returned

to pharmacy for drug accountability prior to destruction according to local practices. Drug accountability and destruction records should be maintained by the local pharmacy.

8.14. AXITINIB MANUFACTURER

Axitinib (also known as AG-013736) is manufactured and provided free of charge by Pfizer to participating centres.

8.15. PACKAGING AND LABELLING

Axitinib is presented as 1mg and 5mg immediate release film-coated tablets and supplied in HDPE (Heavy Duty Polyethylene) bottles, with induction seals. Tablet bottles of each dose contain 60 tablets.

Pfizer will coordinate study drug packaging, labelling and distribution for this trial. The schedule of responsibilities for this arrangement is detailed in a contract between Pfizer and the Co-sponsors.

Labelling will be the responsibility of Pfizer and will be compliant with Annex 13 of the Good Manufacturing Guidelines (GMP) and all applicable local regulatory requirements.

8.16. DRUG STORAGE

Axitinib should be stored in the original package in order to protect from moisture and should be stored at controlled room temperature (between 15°C and 30°C) and protected from light. The local pharmacy is responsible for ensuring that the study medication is stored in an appropriate secured area.

8.17. DISTRIBUTION OF DRUGS TO SITE

ICR-CTSU will arrange for a supply of the study drugs to be sent from Pfizer to the relevant pharmacy department following centre initiation. Local R & D approval and a study agreement must be in place before any drug can be shipped to sites.

8.18. COMMERCIAL SUPPLY

After November 2018 A-PREDICT participants still receiving axitinib will be transferred to free of charge commercial supply. Commercial supply will be provided by Pfizer until A-PREDICT participants' treatment discontinuation.

Commercial supply axitinib will be labelled by the local site's pharmacy prior to dispensing in accordance with the MHRA approved A-PREDICT commercial supply label contents. Axitinib should be stored as per section 8.16 of the protocol.

Pfizer are responsible for distribution of commercial supply axitinib to participating sites.

8.19. PHARMACY RESPONSIBILITIES AND DRUG ACCOUNTABILITY

8.19.1. LABELLING

Pharmacies may add their own hospital dispensing label to the study drug which must not obscure the existing label on the drug packaging.

8.19.2. ACCOUNTABILITY

The local pharmacy department must designate a responsible person for ensuring that:

Version 9 Dated 02/06/2020

- the study drug is handled and stored safely and properly;
- the study drug label is completed for each patient in accordance with Annex 13 of the EU Good Manufacturing Practice (GMP) Guidelines;
- the study drug is dispensed only to trial patients and in accordance with the protocol;
- full accountability of the study drug is maintained
- there is a sufficient supply of study drug for patients' continued treatment, and in a timely manner contact ICR-CTSU for re-supply of stock;
- study drug expiry dates are monitored and are used in order of expiry date order i.e. earliest expiry first;
- unused study drug is destroyed locally in accordance with hospital protocol.

Records must be kept of all deliveries, dispensing and destruction in accordance with the A-PREDICT Pharmacy Guidance Notes. These records may be requested by ICR-CTSU during the trial to monitor supply and usage of stock. Account must be given of any discrepancies and certificates of delivery and return must be signed.

8.20. PATIENT CARDS

Small wallet sized cards will be produced by ICR-CTSU on request by the participating centre. Each card will state:

- the name and emergency contact details of the participating centre
- that the patient is participating in the A-PREDICT trial
- that the patient is taking axitinib

Medical judgement should be exercised in deciding whether other AEs are serious. Important AEs that are not immediately life-threatening or do not result in death or hospitalisation but may jeopardise the subject or may require intervention to prevent one of the other outcomes listed in the definition above, should also be considered serious.

Serious Adverse Reaction (SAR): Any serious adverse event judged by either the Principal Investigator or the Chief Investigator as having suspected causal relationship to the study drug.

Suspected Unexpected Serious Adverse Reaction (SUSAR): Any serious adverse event judged by either the Principal Investigator or the Chief Investigator as having suspected causal relationship to the study drug that is not listed on the SmPC and, in the opinion of the Chief Investigator, is unexpected.

9.2. CAUSALITY

The Principal Investigator and the Chief Investigator must assess whether Serious Adverse Events have a suspected causal relationship to the study drug. A suspected causal relationship is defined as possibly, probably or definitely related (see definitions of causality table).

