7. TRIAL ASSESSMENTS & DISPENSING SCHEDULE

7.1. PRE-REGISTRATION ASSESSMENTS

The following screening procedures must be performed

7.1.1. WITHIN 21 DAYS PRIOR TO TRIAL REGISTRATION:

- Medical history
- Physical examination including ECOG performance status, body weight, height, temperature, blood pressure measurement (repeated twice as per inclusion criteria), heart rate, respiratory rate
- Haematology, coagulation, glucose, renal and liver function, serum calcium and LDH
- Urinalysis for protein
- Serum Thyroid Function Tests (Free T4 and TSH)
- Pregnancy test (serum or urine), if female and of child-bearing potential
- Baseline symptom assessment (NCI CTCAE v.4)
- CT thorax, abdomen and pelvis and tumour assessment using RECIST 1.1 criteria. CT must be conducted prior to the research biopsy.
- Mandatory percutaneous biopsy of non-necrotic region of primary renal tumour under ultrasound or CT guidance (see Appendix B Translational research studies)
- If possible, percutaneous biopsy of one metastatic site under ultrasound or CT guidance (see Appendix B Translational research studies).
- Histological confirmation of metastatic renal cell carcinoma from either site (if not previously confirmed)*.
- Assessment of concomitant medications

*NB If a patient consents to donate research biopsies but is subsequently found to be ineligible, these research biopsies should be notified to ICR-CTSU as described in Section 19.4.1 of the protocol: Tracking of baseline samples for ineligible patients

7.2. BASELINE ASSESSMENTS – PRETREATMENT DAY 1 WEEK 1

The following must be performed on **day 1 week 1** prior to starting the study drug unless conducted within previous 7 days as part of pre-registration assessments:

- Physical examination including ECOG performance status, body weight, temperature, blood pressure, heart rate, respiratory rate
- Haematology, coagulation, glucose, renal and liver function, serum calcium and LDH
- Urinalysis for protein

- Symptom assessment (NCI CTCAE v.4)
- Blood samples and urine sample for biomarker analysis (see Appendix B)
- Assessment of concomitant medications
- Pregnancy test if not conducted within 3 days of starting treatment

Dispense axitinib to patient (see section 8)

7.3. DAY 1 WEEK 3

The following investigations should be conducted on day 1 of week 3 (+/- 72hrs):

- Physical examination including ECOG performance status, body weight, temperature, blood pressure, heart rate, respiratory rate

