- Symptom assessment (NCI CTCAE v.4)
- Serum Thyroid Function Tests (Free T4 and TSH)
- Assessment of concomitant medications

NB. If the participant has any axitinib treatment interruptions \geq 1 week, please contact the trials office for advice on scheduling of subsequent follow up and research biopsy.

7.4. DAY 1 WEEK 5:

The following investigations should be conducted on day 1 of week 5 (+/- 72 hrs):

- Physical examination including ECOG performance status, body weight, temperature, blood pressure, heart rate, respiratory rate
- Haematology, coagulation, glucose, renal and liver function, serum calcium and LDH
- Urinalysis for protein
- Symptom assessment (NCI CTCAE v.4)
- Assessment of compliance with study medication
- Serum Thyroid Function Tests (Free T4 and TSH)
- Assessment of concomitant medications

NB. If the participant has any axitinib treatment interruptions \geq 1 week, please contact the trials office for advice on scheduling of subsequent follow up and research biopsy.

Dispense axitinib to patient (see section 8)

7.5. DAY 1 WEEK 8

Patient should be instructed to stop axitinib 5-7 days prior to biopsy (after 7 weeks of treatment)

NB. If the participant has any axitinib treatment interruptions \geq 1 week, please contact the trials office for advice on scheduling of subsequent follow up and research biopsy.

7.6. DAY 1 WEEK 9

The following investigations/assessments should be conducted on day 1 week 9 (+/- 72 hrs):

- Physical examination including ECOG performance status, body weight, temperature, blood pressure, heart rate, respiratory rate
- Haematology, coagulation, glucose, renal and liver function, serum calcium and LDH
- Urinalysis for protein
- Symptom assessment (NCI CTCAE v.4)
- Blood samples and urine sample for biomarker analysis (see Appendix B)
- CT thorax, abdomen and pelvis and assessment of response according to RECIST 1.1 criteria.
- Percutaneous biopsy of non-necrotic region of primary renal tumour (from same site as first biopsy if possible) via appropriate (US or CT) guidance (see Appendix B)
- Assessment of compliance with study medication (see section 8)
- Assessment of concomitant medications

Dispense axitinib, with instructions to patient to start 2-3 days after biopsy (see section 8)

NB: CT thorax, abdomen and pelvis should be carried out prior to biopsy

7.7. DAY 1 WEEK 13 (AND EVERY 4 WEEKS TO SIX YEARS/DISEASE PROGRESSION):

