9.3. DEFINITIONS OF CAUSALITY

Relationship	Description
Unrelated	There is no evidence of any causal relationship with the trial drug
Unlikely	There is little evidence to suggest there is a causal relationship (e.g. the event did not occur within a reasonable time after administration of the trial medication). There is another reasonable explanation for the event (e.g. the

	patient's clinical condition, other concomitant treatment)
Possible	There is some evidence to suggest a causal relationship (e.g. because the event occurs within a reasonable time after administration of the trial medication). However, the influence of other factors may have contributed to the event (e.g. the patient's clinical condition, other concomitant treatments)
Probable	There is evidence to suggest a causal relationship, and the influence of other factors is unlikely
Definitely	There is clear evidence to suggest a causal relationship, and other possible contributing factors can be ruled out
Not assessable	There is insufficient or incomplete evidence to make a clinical judgement of the causal relationship.

If there is any doubt about the causality of an event, the investigator should contact ICR-CTSU who will discuss with the Chief Investigator. The drug manufacturer and/or other clinicians may also be asked for advice.

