9.9. ANNUAL REPORTING OF SERIOUS ADVERSE REACTIONS

An annual report will be provided to the MHRA and the Main REC by ICR-CTSU and copied to the sponsors at the end of the reporting year. This will be defined as the anniversary of the date when the Clinical Trials Authorisation (CTA) was obtained. This will include all related events reported on SAE forms, and a report from the Independent Data Monitoring and Steering Committee (IDMSC).

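### SAE causality is rated only against axitinib, so serious harm attributed solely to a trial biopsy is not identified as such and need not be listed in the annual report

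*Combined protocol and SAP*

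**What the plan says.** **Causality.** Section 9.2 states: "The Principal Investigator and the Chief Investigator must assess whether Serious Adverse Events have a suspected causal relationship to the study drug". It then fixes what counts as related: "A suspected causal relationship is defined as possibly, probably or definitely related (see definitions of causality table"). The scale in 9.3 is anchored to the trial drug. 'Unrelated', for example, reads "There is no evidence of any causal relationship with the trial drug", and 'Unlikely' takes in events with another reasonable explanation. No category concerns a trial procedure. Section 9.1 defines a serious adverse reaction in the same way: "Any serious adverse event judged by either the Principal Investigator or the Chief Investigator as having suspected causal relationship to the study drug". Expedited reporting (9.6, 9.7) is also triggered by the drug alone.

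**Annual report.** On events, section 9.9 says: "This will include all related events reported on SAE forms". The same sentence adds a report from the IDMSC.

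**Biopsies.** Before registration, section 7.1.1 requires: "Mandatory percutaneous biopsy of non-necrotic region of primary renal tumour under ultrasound or CT guidance". Section 7.6 repeats the primary-tumour biopsy at week 9, and 7.9 schedules another biopsy at progression. A metastatic biopsy at baseline is optional (19.3.2). Willingness to have tumour biopsies is an entry condition (5.3, criterion 15).

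**Capture.** Section 9.5 starts SAE reporting at registration and ends it 28 days after the last dose. The definition in 9.1 ties an SAE to the 28 days around receipt of study drug.

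**The concern.** The trial exposes patients to two sources of risk: axitinib, and invasive sampling done largely for the translational study. The safety rules attribute harm to the first only. A serious complication that the investigator puts down wholly to the needle is correctly answered as not drug-related, and the plan then asks nothing further about its cause. It need not appear among the events sent to the regulator and ethics committee, and the toxicity summary in 10.2.2 does not separate it from other events.

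At stake is whether the trial can state directly how often a research biopsy caused serious harm. An ethics committee needs that figure to judge whether the repeat biopsies remain justified. The primary endpoint, its estimate and the two-stage decision rule are not affected.

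**Working it through.** The plan gives no biopsy complication rate, so there is no figure of its own to reproduce. The check follows three kinds of event through the rules, then sizes the result.

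**1. Tracing the rules**

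| Event | SAE form under 9.1 and 9.5? | Rating under 9.3 | Related under 9.2? | Required among the events in 9.9? | Identified as procedural? |
|---|---|---|---|---|---|
| Serious harm after a week 9 or progression biopsy, attributed solely to the biopsy | Yes | 'Unrelated' or 'Unlikely' | No | No | No |
| The same, with a drug contribution suspected | Yes | 'Possible' or higher | Yes | Yes, as a drug reaction | No |
| Acute harm after the baseline biopsy, before registration | Possibly none | Not reached | Not reached | No | No |

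The progression biopsy normally falls inside the capture window. It is planned one week after stopping axitinib (7.9), which leaves 28 − 7 = 21 days of reporting after it.

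**2. In-window procedures**

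Inputs: 99 patients (5.1) and two scheduled biopsies after registration, at week 9 and progression (7.6, 7.9).

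Maximum number of procedures = 99 × 2 = 198.

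The serious complication rate per procedure, r, is an assumption. Expected events = 198 × r. The chance of at least one, treating procedures as independent, is 1 − (1 − r)^198.

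- r = 1%: 198 × 0.01 = 1.98 events; chance of at least one 86%.
- r = 3%: 198 × 0.03 = 5.94 events; chance of at least one 99.8%.

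That is about 2–6 events. It is an upper bound for three reasons:

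- Patients who stop before week 9, or never have a progression biopsy, contribute fewer procedures.
- A patient who stops axitinib early and progresses more than 28 days later has the progression biopsy outside the window.
- Events rated 'Possible' or higher do enter the annual report, although not as procedural harm.

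**3. Baseline biopsies, counted separately**

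At the same assumed rates, 99 × 0.01 = 0.99 and 99 × 0.03 = 2.97, so about 1–3 further events. These precede registration, so the likely loss is the absence of an SAE form and not its causality coding. They should not be added to the 198.

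**The case against.** The strongest reply is that section 9 is a pharmacovigilance section and does its own job. 'Unrelated to the drug' is the right answer for an event caused only by a needle, and 9.9 is headed as a report of serious adverse reactions, which 9.1 defines by the drug. This stands. What is missing is a second question; the existing one is not answered wrongly.

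Four stronger readings that a reader might infer are not supported:

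- **Every bleed after the week 9 biopsy must be rated not related.** The 'Possible' category allows for other contributing factors, section 8.4.1 treats bleeding as a potential axitinib-related event, and dosing restarts 2–3 days after the biopsy (8.1). Such a bleed could be rated 'Possible' and reported.
- **Biopsy harm escapes oversight.** Every reported SAE goes to the trials unit within 24 hours (9.5), is assessed by the Chief Investigator and is forwarded to the manufacturer (9.6). The independent committee reviews safety about every six months (10.3), and its report accompanies the annual report (9.9). None of these steps, however, requires attribution to a procedure.
- **A biopsy complication rate could never be obtained.** Toxicities are MedDRA-coded (10.2.2) and sample collection is logged (19.4), so events might be matched to biopsies afterwards. The SAE form is not reproduced in the protocol, and the flow diagram in 9.9.1 could not be checked. The text itself plans no such matching.
- **All three biopsies count, giving 99 × 3 = 297 procedures and about 3–9 miscoded SAEs at 1–3%.** The baseline biopsy comes before SAE reporting opens, so its acute harm would mostly not be coded at all. It also supplies the diagnostic core (19.3.1, 19.4.1), so its risk is not wholly added by the research.

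**Conclusion.** The point holds within limits. Under the plan as written, an SAE attributed solely to a trial biopsy falls outside the related events that 9.9 requires. One with a suspected drug contribution is reported, but as a drug reaction. In neither case does the plan's text call for the procedure to be identified as a cause. The loss is structured attribution and guaranteed reporting to the MHRA and ethics committee, with other oversight intact.

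The size is at most 198 in-window procedures and about 2–6 events. This rests on all 99 patients having both biopsies and on the assumed 1–3% rate, for which the documents offer no source. A separate and possibly wider gap concerns acute harm from the baseline biopsy, which may generate no SAE form.

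This is worth correcting because it is cheap and bears on the justification for repeat biopsies. It does not weaken the efficacy analysis.

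**What to change.** - **Sections 9.2, 9.3 and the SAE form:** add a separately scored item for relationship to a trial-mandated procedure, on the existing scale, alongside the drug item.
- **Section 9.9:** include SAEs related to a trial procedure as well as those related to the drug.
- **Sections 9.1 and 9.5:** start capture of procedure-related SAEs at consent or the first research biopsy, so that the baseline biopsy is covered.
- **Section 10.2.2:** tabulate serious biopsy complications with the number of procedures as denominator, separately for baseline, week 9 and progression.

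The cost is one form item, a wording amendment and a short retrospective review of SAEs already reported around biopsies. The review is needed because the protocol is at version 9 (June 2020) and provides for patients beyond six years on treatment, so many biopsies have probably been done already. No new visits, staff or procedures are required.

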9.3. DEFINITIONS OF CAUSALITY

Relationship	Description
Unrelated	There is no evidence of any causal relationship with the trial drug
Unlikely	There is little evidence to suggest there is a causal relationship (e.g. the event did not occur within a reasonable time after administration of the trial medication). There is another reasonable explanation for the event (e.g. the

	patient's clinical condition, other concomitant treatment)
Possible	There is some evidence to suggest a causal relationship (e.g. because the event occurs within a reasonable time after administration of the trial medication). However, the influence of other factors may have contributed to the event (e.g. the patient's clinical condition, other concomitant treatments)
Probable	There is evidence to suggest a causal relationship, and the influence of other factors is unlikely
Definitely	There is clear evidence to suggest a causal relationship, and other possible contributing factors can be ruled out
Not assessable	There is insufficient or incomplete evidence to make a clinical judgement of the causal relationship.

If there is any doubt about the causality of an event, the investigator should contact ICR-CTSU who will discuss with the Chief Investigator. The drug manufacturer and/or other clinicians may also be asked for advice.

